### 1.10 Rationale for Inclusion of Patients with Stable Disease

SRT is often used clinically in individuals who have not had progression of disease, but who may still benefit from radiation. Some situations when this would be appropriate include but are not limited to:

- Metastatic sites that, if left to grow, would cause clinical issues but are currently asymptomatic, such as spinal metastases that could cause cord compression
- Metastatic sites that are causing symptoms such as pain, neurological changes, shortness of breath, hemoptysis, or rectal bleeding
- Oligoprogressive metastasis in which most of the metastatic sites have responded to immunotherapy but one or more has grown larger.

Recent studies indicate that the combination of the immunotherapy drugs and SRT is well tolerated, with toxicity similar to monotherapy ([89-91](#)). Preliminary results also indicate the presence of abscopal response in non-irradiated measurable lesions with concurrent pembrolizumab([90](#)). Another study suggested that the addition of RT to immune therapy could “allow for a prolonged response to immune checkpoint inhibition” ([92](#)).

Given the apparent low risk of combining immunotherapy with SRT, we have elected to expand the study population beyond those patients who have responded to and then progressed on immunotherapy, to include patients who have demonstrated disease control with immunotherapy but are no longer continuing to improve. In these cases, radiotherapy may provide improved disease control and symptom management. We will continue to explore the potential synergistic interactions of the immune-mediated abscopal effect with the anti-PD-1/PD-L1 activity of the allowed immunotherapy drugs.

## **2 OBJECTIVES**

### **2.1 Primary Objective**

To determine if SRT and PD-1/PD-L1 inhibiting therapy can restore the benefit of PD-1/PD-L1 inhibiting therapy in patients with an advanced solid tumor who had demonstrated disease control from PD-1/PD-L1 inhibiting therapy but did not continue to improve

### **2.2 Secondary Objectives**

In patients who have received study treatment (SRT and PD-1/PD-L1 inhibitor):

- 2.2.1 To determine the response rate of SRT and PD-1/PD-L1 inhibiting therapy per unidimensional immune-related response criteria (irRC) and, if brain metastases are present, per iRANO
- 2.2.2 To determine the response rate at irradiated tumor sites
- 2.2.3 To determine the response rate at non-irradiated tumor sites
- 2.2.4 To determine the 2-year survival rate
- 2.2.5 To assess the toxicity associated with the study treatment
- 2.2.6 To assess the radiobiological and immunological characteristics of patients receiving study treatment using blood samples collected before and after SRT

### **2.3 Exploratory Objectives**

- 2.3.1 To explore the use of volumetric measurements of tumor size for assessing response in patients who have received study treatment.

## **3 STUDY DESIGN**

### **3.1 General Description**

This study is a phase 2 single-arm clinical trial of SRT delivered concurrently with PD-1 or PD-L1 inhibiting therapy to determine if standard SRT potentiates the abscopal effect of PD-1 or PD-L1 inhibiting therapy in patients with an advanced solid tumor who previously achieved disease control from PD-1 or PD-L1 inhibiting therapy but are no longer continuing to improve. Eligible patients must have 1 to 5 metastatic, recurrent, or primary tumors that are clinically appropriate to receive SRT and at least one additional tumor that is measureable but will not be treated using SRT.

SRT will be delivered over 1 to 2 weeks. Patients will continue to receive the same FDA-approved PD-1 or PD-L1 inhibitor that they had been receiving previously until 52 weeks following completion of SRT.

Correlative blood samples will be collected at baseline, prior to the second SRT fraction, after the last SRT fraction (on the same day), and at 8, 24, and 52 weeks after the last SRT fraction. These samples will be used to determine the mechanistic immunologic effects of therapy.

### 3.2 Study Accrual

A Simon two-stage design will be employed to assess for treatment futility by examining treatment response in the first 11 patients at the 24-week post-SRT time point. If at least one patient has improved disease control, accrual will continue until a total of 41 patients have been enrolled in the study. Given the established safety profile of PD-1 pathway inhibition and SRT, an interruption in accrual after the first 11 patients have been accrued will not be required.

Refer to Section [1.6](#) and Section [13.2](#) for accrual restrictions for patients who receive SRT to brain metastases alone.

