### 13.2 Sample Size and Accrual Rate

Given that only approximately 10% of patients who continue PD-1 or PD-L1 inhibition after progression or plateau on a prior PD-1 or PD-L1 inhibiting agent experience improved disease control ([18](#), [45](#), [98](#)), we would consider an improved disease control rate of 25% (relative to 10% of patients who do not receive radiotherapy) with the combination of SRT and PD-1 or PD-L1 inhibiting therapy to be promising and worthy of further study. To statistically test whether the disease control improvement rate meets our disease control criteria, the study will require a sample size of 42 evaluable patients to have 80% power at 5% level of significance. We anticipate that 10% of enrolled patients may be inevaluable; therefore, up to 46 patients are required to ensure that sufficient patients will be evaluable. Patients who are not evaluable for efficacy as defined in Section [13.5.2](#) will be replaced.

Given the limited data on the immunogenicity of brain metastases, enrollment of patients who receive SRT to brain metastases alone will be limited to no more than 4 of the first 14 evaluable patients and no more than 11 of the 37 evaluable patients. Patients who receive SRT to other sites as well as to brain metastases will not be counted towards this allotment.

Accrual is anticipated to be about 1 patient every 1-2 months over a period of about 4.5 years.

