### 13.3 Statistical Analysis of Primary Objective

We will employ a Simon two-stage design to assess for treatment futility by examining the rate of improved disease control at 24 weeks following completion of SRT. Therefore, 14 patients will be evaluated for the primary endpoint (ie, improved disease control) at 24 weeks. If at least 2 successes are observed, we will continue to recruit a total of 42 evaluable patients. If fewer than 2 successes are observed, then the study will close to further accrual. If 8 or more success are observed in the total population of 42 evaluable patients, further investigation of this treatment regimen will be considered warranted.

At the end of the first stage, all primary and secondary endpoints will be summarized and shared with the Data Safety and Monitoring Committee (DSMC). If the study goes into the second stage of accrual, this will be the interim analysis. If early termination of the study is recommended, this will be the final analysis.

The rate of improved disease control will be reported with a point estimate and 95% confidence interval. Analysis of the primary objective will include all efficacy-evaluable patients; however, a subset analysis of efficacy-evaluable patients who only receive SRT to brain metastases will also be performed.

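### Section 3.2 states a different stage-1 rule and total (at least 1 success in 11 patients, 41 enrolled) from Section 13.3 (at least 2 in 14, 42 evaluable), and the brain-only cap in 13.2 uses a total of 37 that matches neither

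*Combined protocol and SAP*

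**What the plan says.** Section 3.2 (Study Accrual) describes a Simon two-stage design for futility, "examining treatment response in the first 11 patients at the 24-week post-SRT time point". It continues: "If at least one patient has improved disease control, accrual will continue until a total of 41 patients have been enrolled in the study". It gives no success threshold for the end of the trial. It adds that accrual need not pause once the first 11 patients are in. Its pointer to Section 13.2 concerns only the brain-only accrual restriction.

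Section 13.3 describes the same futility assessment at the same 24-week time point, but on 14 patients: "If at least 2 successes are observed, we will continue to recruit a total of 42 evaluable patients". Fewer than 2 successes closes accrual. Eight or more successes in 42 evaluable patients would warrant further investigation. The stage-1 summary goes to the data and safety monitoring committee.

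Section 13.2 gives the basis, with a 10% reference rate and a 25% target rate: "the study will require a sample size of 42 evaluable patients to have 80% power at 5% level of significance". On enrolment it says "We anticipate that 10% of enrolled patients may be inevaluable", and "therefore, up to 46 patients are required to ensure that sufficient patients will be evaluable". It also says that patients not evaluable for efficacy will be replaced. It then limits patients who receive stereotactic radiotherapy to brain metastases alone to "no more than 4 of the first 14 evaluable patients and no more than 11 of the 37 evaluable patients".

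**The concern.** Sections 3.2 and 13.3 are both current text and both claim to be the trial's Simon stage-1 rule. They cannot be read as two complementary looks, because the stage-1 size, the number of successes needed and the total all differ. The study team is likely to look for the accrual rule in Section 3.2, while the statistician will use 13.3. If exactly one success is seen and it falls among the first 11 patients, 3.2 says continue and 13.3 says close. The monitoring committee would then hold two rules for one dataset. A choice made after the data are known would not have the error rates that the plan states.

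The totals conflict as well. The like-for-like comparisons are 41 against 46 enrolled (3.2 against 13.2), and 37 against 42 evaluable (the cap in 13.2 against the sample size in 13.2 and 13.3).

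**Working it through.** **Inputs.** Reference rate 10%, target rate 25%, level 5%, power 80%, 42 evaluable, 10% inevaluable, 46 enrolled (13.2). Stage 1 of 14, continue on 2 or more, success at 8 or more of 42 (13.3). Stage 1 of 11, continue on 1 or more, 41 enrolled (3.2). The 5% is taken as one-sided, as is usual for a Simon design; the plan does not state sidedness.

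**1. Does the 13.3 design reproduce?** For stage-1 size n1, continue threshold g, total n and final threshold r, the probability of declaring success at true rate p is

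sum over x from g to n1 of P(Bin(n1, p) = x) × P(Bin(n − n1, p) ≥ r − x).

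With n1 = 14, g = 2, n = 42, r = 8:
- p = 0.10: 0.0464
- p = 0.25: 0.8042

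The stated 5% and 80% are met.

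**2. Probability of stopping at stage 1.**
- 13.3 (0 or 1 of 14): (1−p)^14 + 14p(1−p)^13. At 10%: 0.2288 + 0.3559 = 0.585. At 25%: 0.0178 + 0.0832 = 0.101.
- 3.2 (0 of 11): (1−p)^11. At 10%: 0.314. At 25%: 0.042.

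**3. Opposite decisions on the same 14 patients.** This takes both rules as applied to evaluable patients in the same order; 3.2 does not say whether its 11 must be evaluable.
- 3.2 continues, 13.3 stops: exactly one success in 14, and it is among the first 11. Probability 11p(1−p)^13.
- 3.2 stops, 13.3 continues: none in the first 11, then at least 2 in the next 3. Probability (1−p)^11 × [3p²(1−p) + p³].

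| True rate | 3.2 continues, 13.3 stops | 3.2 stops, 13.3 continues | Total |
|---|---|---|---|
| 10% | 0.2796 | 0.0088 | 0.2884 |
| 25% | 0.0653 | 0.0066 | 0.0719 |

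Given that 13.3 stops, 3.2 continues with probability 0.2796/0.5846 = 47.8% at 10%, and 0.0653/0.1010 = 64.7% at 25%.

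**4. What the totals imply.** 41 × 0.9 = 36.9 evaluable; 46 × 0.9 = 41.4; 42/0.9 = 46.7. With the same formula and r = 8:

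| Stage 1 | Evaluable total | Type I error | Power |
|---|---|---|---|
| 14, at least 2 | 42 | 4.64% | 80.4% |
| 14, at least 2 | 41 | 4.16% | 78.9% |
| 11, at least 1 | 41 | 4.52% | 81.9% |
| 14, at least 2 | 37 | 2.51% | 70.8% |
| 11, at least 1 | 37 | 2.65% | 72.7% |

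Only the first row is a design that the protocol states in full. The others show what follows if 41 is read as an evaluable total, or as an enrolment ceiling that leaves 37.

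**5. The cap.** 4/14 = 28.6% and 11/37 = 29.7%. The 14 agrees with 13.3; the 37 agrees with no evaluable total stated elsewhere.

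**The case against.** The strongest reply is that Section 13 is the statistical section, that it holds a complete design which works, and that 3.2 is plainly leftover text that no statistician would follow. Part of this stands: the 42-patient calculation is correct. But nothing in the protocol gives Section 13 precedence, and 3.2 is worded as an operating instruction.

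Four stronger readings are tempting, and the documents do not support them.

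- *Only the 13.3 numbers can meet 5% and 80%.* With 8 successes required of 41 evaluable, the 3.2 numbers would give 4.52% and 81.9%. What 3.2 lacks is a stated final threshold, and its 41 is an enrolled total.
- *Under 3.2 the trial would usually continue where 13.3 stops it.* At a 10% rate this happens slightly less than half the time (47.8%). It exceeds half at 25%, where 13.3 seldom stops.
- *The trial would have only 71–73% power.* That needs 41 to act as a hard enrolment ceiling with no replacement. Sections 13.2 and 13.5.2 replace inevaluable patients. With 41 evaluable, power is 79–82%.
- *There are three competing designs.* The 37 appears only as the denominator of the cap, with no stage-1 rule or threshold attached. Since 41 × 0.9 = 36.9, both figures may come from one superseded design, but that is inference.

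Expected sample sizes are not compared here. The 3.2 total counts enrolled patients and the 13.3 total evaluable ones, and 3.2 lets accrual run on while stage 1 matures.

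**Conclusion.** The contradiction is real and affects a decision rule, so it must be fixed. The two stage-1 rules disagree in 28.8% of trials at a true rate of 10%, and almost all of that is 3.2 continuing where 13.3 closes. They disagree in 7.2% of trials at 25%. At 10%, following 3.2 would cut the chance of early stopping from 58.5% to 31.4%. These figures assume independent patients with a common success rate and both rules applied to the same evaluable patients in order.

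The defect is confined to the text of 3.2 and the 37 in 13.2. The 13.3 design delivers what the plan claims for it. Any loss of power from the 41 is conditional on how that figure would be applied, and ranges from none to about 10 percentage points (80.4% to 70.8%).

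**What to change.** - **Section 3.2:** replace the stage-1 size, continue rule and total with those of 13.3 (14 evaluable patients, at least 2 successes to continue, 42 evaluable in total). Give the enrolment ceiling of 13.2 (up to 46, inevaluable patients replaced). Change the 11 in the sentence about not interrupting accrual to 14.
- **Section 13.2:** restate the second part of the brain-only cap against 42 evaluable patients, with the sponsor confirming the number. Twelve of 42 would keep the 4-of-14 proportion (12/42 = 28.6%), but it is only one option.
- **Optional:** 42/0.9 = 46.7 rounds up to 47 rather than 46. This is a rounding matter that replacement already covers.

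The cost is an amendment to the wording of two sections. It needs no patients beyond those that 13.2 and 13.3 already require, and the design does not have to be recalculated.

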### 3.3 Primary Endpoint

Proportion of patients with improved disease control (see Section [13.1](#)) per Response Evaluation Criteria in Solid Tumors Version 1.1 (RECIST v1.1) and, if brain metastases are present, per Response Assessment in Neuro-Oncology for Brain Metastases (RANO-BM) criteria at 24 weeks following SRT

### 3.4 Secondary Endpoints

- 3.4.1 Proportion of patients alive and free from progression (ie, CR, PR, or SD) per unidimensional irRC and, if brain metastases are present, per iRANO criteria at 24 weeks following SRT
- 3.4.2 Proportion of patients with treatment response (ie, CR, PR, or SD) at irradiated tumor sites at 24 weeks following SRT (refer to Section [10.1](#) for response criteria)
- 3.4.3 Proportion of patients with treatment response (ie, CR, PR, or SD) at non-irradiated tumor sites at 24 weeks following SRT (refer to Section [10.1](#) for response criteria)
- 3.4.4 Proportion of patients who are alive at 2 years after completion of SRT
- 3.4.5 Adverse events including the following:
  - All SRT-related and immunotherapy-related  $\geq$  grade 3 adverse events per the most current National Cancer Institute (NCI) Common Terminology Criteria for Adverse Events Version 5.0 (CTCAE v5.0) occurring from initiation of SRT until 8 weeks after the last SRT fraction
  - All immunotherapy-related adverse events (AEs) occurring from 8 weeks post-SRT until 2 years post-SRT requiring discontinuation of PD-1 or PD-L1 inhibiting therapy and concurrent initiation of immunosuppressive agents such as steroids as described in Section [8.5.2](#).

- 3.4.6 Radiobiological signature as described in Section [1.9.3](#) using blood samples collected prior to SRT (baseline), prior to the 2nd SRT fraction, immediately following completion of SRT (on same day); and at 8, 24, and 52 weeks following completion of SRT

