4.1.1 Pathologically-proven diagnosis of a solid tumor malignancy

4.1.2 One of the following criteria must be met:

- 4.1.2.1 Clinical or radiographic evidence of disease control (defined as best response of SD or PR or combination of both for  $\geq 16$  weeks) without evidence of CR or progression

**OR**

- 4.1.2.2 Clinical or radiographic evidence of disease progression during treatment with PD-1 or PD-L1 inhibiting therapy, following previous tumor response (CR, PR, or SD for  $\geq 16$  weeks) to PD-1 or PD-L1 inhibiting therapy,

**and**, for patients who discontinued PD-1 or PD-L1 inhibiting therapy during response to therapy, disease progression must have occurred following at least 8 weeks of re-treatment with PD-1 or PD-L1 inhibiting therapy

Note: Both the treating medical oncologist and radiation oncologist must be in agreement with determination of disease progression.

4.1.3 Administration of a PD-1 or PD-L1 inhibitor within 60 days prior to study registration

4.1.4 Determination by the treating radiation oncologist that the patient is a candidate for SRT (ie, radiation therapy with a stereotactic setup)

Note: All brain metastases will receive SRT.

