## 13 STATISTICAL CONSIDERATIONS

### 13.1 Study Design

This is a single-arm phase 2 study of SRT and PD-1 or PD-L1 inhibiting therapy for patients with advanced solid tumors who achieved disease control during PD-1 or PD-L1 inhibiting therapy. The primary objective is to determine if SRT can restore the benefit of PD-1 or PD-L1 inhibiting therapy in patients with an advanced solid tumor who had disease control from PD-1 or PD-L1 inhibiting therapy but did not continue to improve. For patients enrolled with progression, this would mean SD, PR, or CR. For patients enrolled with stable or plateaued disease, restoration of benefit would be an objective response, ie PR or CR.

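### Site-level response endpoints 3.4.2 and 3.4.3 count stable disease as response even for patients who enter with stable disease

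*Combined protocol and SAP*

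**What the plan says.** Section 3.4 defines the two site-level endpoints in parallel: "Proportion of patients with treatment response (ie, CR, PR, or SD) at irradiated tumor sites at 24 weeks following SRT" (3.4.2) and "Proportion of patients with treatment response (ie, CR, PR, or SD) at non-irradiated tumor sites at 24 weeks following SRT" (3.4.3). Both refer to Section 10.1 for criteria, and neither distinguishes patients by disease status at entry. The matching objectives use the word response without qualification; 2.2.3 reads "To determine the response rate at non-irradiated tumor sites".

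Eligibility has two routes. Criterion 4.1.2.2 takes patients who progressed after earlier benefit. Criterion 4.1.2.1 takes patients with disease control, "defined as best response of SD or PR or combination of both for" at least 16 weeks, and with neither CR nor progression.

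Section 13.1 treats the two routes differently for the primary objective. "For patients enrolled with progression, this would mean SD, PR, or CR"; but "For patients enrolled with stable or plateaued disease, restoration of benefit would be an objective response, ie PR or CR".

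Section 13.4 plans one subset for the secondary objectives, patients irradiated only in the brain. The registration subgroups in Section 6.2 follow the irradiated site, not the entry route.

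**The concern.** A patient who enters stable and whose tumors stay the same size is a failure under 13.1 but a responder on both 3.4.2 and 3.4.3. No other section corrects this, and the share of stable entrants is not capped.

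Section 3.1 states the trial's aim as "to determine if standard SRT potentiates the abscopal effect of PD-1 or PD-L1 inhibiting therapy", and 3.4.3 is the proportion that bears on it at site level. These patients had at least 16 weeks of control and continue the same drug. Without a control arm, stable disease that persists in them cannot be told apart from continued drug effect. A response rate that includes it depends partly on who was enrolled. Section 13.3 also sends the secondary endpoints to the DSMC after stage 1, so the label matters at the interim as well.

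**Working it through.** **The plan's own figure.** The documents give no number for 3.4.2 or 3.4.3. The only stated figure is for the primary endpoint (13.2, 13.3): 10% versus 25%, 42 evaluable patients, 80% power, 5% significance, continue with at least 2 successes in 14, success with at least 8 in 42. The exact probability of success at true rate p is

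Σ (x = 2 to 14) P[Bin(14, p) = x] × P[Bin(28, p) ≥ 8 − x].

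This gives 0.0464 at p = 0.10 and 0.8042 at p = 0.25, so the stated design reproduces. It uses the primary endpoint only.

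**One patient, two definitions.**

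| Entry route | Status at 24 weeks | Primary endpoint (13.1) | 3.4.2 / 3.4.3 |
|---|---|---|---|
| Stable (4.1.2.1) | SD | failure | response |
| Stable (4.1.2.1) | PR or CR | success | response |
| Progressing (4.1.2.2) | SD, PR or CR | success | response |

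The definitions part only in the first row.

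**Size of the difference.** Let

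- f = share of evaluable patients who enter stable;
- r = probability that a stable entrant has CR or PR at the sites in question at 24 weeks;
- s = probability that a stable entrant is still only SD there;
- q = probability that a progressing entrant has CR, PR or SD there.

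Rate as written in 3.4.3: f(r + s) + (1 − f)q.
Rate under the 13.1 logic: f·r + (1 − f)q.
Difference: f × s.

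The documents give neither f nor s. Assumed ranges, in percentage points:

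| | s = 0.3 | s = 0.5 | s = 0.7 |
|---|---|---|---|
| f = 0.25 | 7.5 | 12.5 | 17.5 |
| f = 0.50 | 15.0 | 25.0 | 35.0 |
| f = 0.75 | 22.5 | 37.5 | 52.5 |

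At f = s = 0.5 this is 0.25 × 42 = 10.5 patients. If f = 0 it is zero. For scale only, set r = q = 0.10, borrowing the primary endpoint's null rate. The 13.1-type rate is then 10% (4.2 of 42), and 3.4.3 would report 17.5% to 62.5% (7.4 to 26.2 of 42).

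The excess always grows with f. The whole 3.4.3 rate grows with f when r + s > q, that is, when stable entrants are more likely than progressing ones to be free of progression at those sites. The same algebra applies to 3.4.2 with its own s.

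**Would applying 13.1 to these endpoints cure it?** Not fully. Section 13.1 sorts patients, while 3.4.2 and 3.4.3 concern sites. Section 1.10 describes oligoprogression, where most sites have responded and one or more has grown. If such a patient enrols under 4.1.2.2 and the growing lesion is irradiated, the non-irradiated sites were controlled at entry. Unchanged SD there would still count as response. Separating SD from CR+PR avoids this. The gap between the two reported rates is then f·s + (1 − f)·t, where t is the probability of SD at those sites among progressing entrants, so it is at least f × s.

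**The case against.** The strongest reply is that the two definitions serve different purposes. Section 13.1 defines success for the primary objective. Section 3.3 refers to it, whereas 3.4.2 and 3.4.3 refer to 10.1. A reader might infer that the secondary endpoints contradict 13.1; they do not, because no text says they must follow it. This stands, and the point is an inconsistency of logic.

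Second, the definition is open. SD is named inside both endpoints, and 4.1.2.2 also includes SD within earlier tumor response. That is true, but 4.1.2.2 describes benefit from the drug before entry. It gives no ground for crediting SRT with stable disease already present.

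Third, a reader might infer that 3.4.3 is the only evidence on an abscopal effect. It is not. Section 13.4 plans time to progression at a non-irradiated site, and the non-irradiated disease required by 4.1.6 enters the RECIST primary endpoint. Time to progression, however, describes delay of growth and not regression.

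Fourth, Section 1.10 gives better disease control as a reason for enrolling stable patients, so remaining progression-free at those sites is relevant. That supports keeping CR+PR+SD under the name disease control. Section 13.4 also lists and summarizes clinical response, so CR+PR could be recovered, but no split by entry route is specified.

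**Conclusion.** The point holds as a matter of definition and reporting. As labelled, 3.4.2 and 3.4.3 count unchanged disease in stable entrants as response, which limits what the trial can conclude about response at non-irradiated sites. The direction is certain once any stable entrant remains SD. The size is not: 7.5 to 52.5 percentage points rests wholly on the assumed ranges for f and s. A reader might take the 25 points at f = s = 0.5 as an estimate; it is one assumed case.

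A reader might also infer that the go/no-go decision is affected. It is not. The Simon rule uses the primary endpoint, and no null rate or threshold attaches to 3.4.2 or 3.4.3. The change should be made before these rates are reported, but it is not a fault in the sample size.

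**What to change.** - In 3.4.2 and 3.4.3, and in objectives 2.2.2 and 2.2.3, define response as CR+PR relative to the pre-SRT baseline at those sites.
- Report CR+PR+SD separately as the 24-week site-level disease control rate.
- Record the entry cohort (4.1.2.1 or 4.1.2.2) at registration, and tabulate both rates and the primary endpoint by cohort.
- Reword objective 2.2.1 as a 24-week progression-free rate. Endpoint 3.4.1 already describes it that way; only the objective calls it a response rate.

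The cost is a few lines of definition, one field at registration and one extra table split. No new assessments are needed: baseline and 24-week disease assessments are already scheduled (10.2.1), and the entry criterion has to be established for eligibility. The reported response rate will be less favourable, and the cohort tables will be small and descriptive.
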